## **9.2 Sample size**

The sample size was based on an ability to detect a relative group difference in FLT SUV (baseline versus interim) of 0.124 and standard deviation of 0.17. A sample size of 15 patients was calculated using a two-sided paired t test, power of 80 %, and the type I error rate was set to be 0.05. The expected response to therapy was assumed to be 20%.

Five patients were added to the sample size to compensate for dropout and no uptake on the baseline scan, leading to a total sample size of 20.

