## **9.3 Data Analyses Plans**

Primary outcome variable: The difference in SUVmax, SUVpeak and proliferative tumor volume between baseline and 2 cycles of chemotherapy will be correlated with overall survival at 1 and 2 years and with progression free survival at 6 months and at 1 year.

The primary outcome of the study is to establish which degree of change in the PET/CT quantitative parameters can predict patients overall survival and progression free survival. The SUVmax (representing the single voxel with the highest activity concentration), SUV peak (which is defined as the average SUV within a 1 cubic cm volume within the region of the tumor with the highest metabolic activity) and proliferative tumor volume of the pancreatic tumor will be measured.

Univariate and multiple cox regression model are going to be used. P-value less than 0.05 will be considered as statistical significant.

Secondary outcome variable: the difference in SUVmax, SUVpeak and proliferative tumor volume between baseline and 2 cycles of chemotherapy will be correlated with binary tumor outcome measured from MRI/CT (resectable versus non-resectable disease) at 6 month using logistic regression. A multiple logistic regression with stepwise selection algorithm will be used to select the most correlated variable(s). Areas under the ROC curve (AUC) and corresponding 95% confidence interval will be calculated for all models. Leave one out cross validation will be applied to avoid over-fit.

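### Stepwise selection among three overlapping FLT parameters in 15 to 20 patients gives an optimistic AUC and an under-covering 95% interval for the secondary 6-month resectability outcome

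*Combined protocol and SAP*

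**What the plan says.** All of this stands in section 9.3 (Data Analyses Plans) unless noted.

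- Secondary outcome: "the difference in SUVmax, SUVpeak and proliferative tumor volume between baseline and 2 cycles of chemotherapy will be correlated with binary tumor outcome", namely resectable or non-resectable disease on MRI or CT at 6 months, by logistic regression.
- Selection: ("A multiple logistic regression with stepwise selection algorithm will be used to select the most correlated variable(s"). No entry or stay criterion is given. The only threshold in the section, P below 0.05, is stated with the Cox models.
- Performance: "Areas under the ROC curve (AUC) and corresponding 95% confidence interval will be calculated for all models". The interval method is not named.
- Validation: "Leave one out cross validation will be applied to avoid over-fit". The plan does not say whether the stepwise step is repeated in each fold, or whether the reported AUC and interval are apparent or cross-validated.
- Overlap: SUVmax is the single hottest voxel, and SUVpeak is the "average SUV within a 1 cubic cm volume within the region of the tumor with the highest metabolic activity".
- Size (section 9.2): "A sample size of 15 patients was calculated using a two-sided paired t test", raised to 20 for dropout and absent baseline uptake.

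The primary analysis is univariate and multiple Cox regression, with no stepwise step stated. The Study Summary mentions AUC and leave-one-out but not stepwise selection.

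**The concern.** When the same few patients choose the predictor and then measure its accuracy, the AUC is biased upward. An ordinary interval treats the model as fixed in advance, so it ignores the choice. Cross-validating a model already chosen on all patients leaves the selection in place. In addition, two of the three candidates measure nearly the same thing, so a ranking between them is mostly noise. At stake is whether a chance finding on resectability could be reported as a cross-validated FLT predictor, with an interval that looks more certain than it is.

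**Working it through.** **1. The plan's own figure.** Section 9.2 assumes a "relative group difference in FLT SUV (baseline versus interim) of 0.124 and standard deviation of 0.17", so the standardized difference is 0.124/0.17 = 0.729. The normal approximation gives n = [(1.96 + 0.84) × 0.17/0.124]² = 14.75, so 15, as stated. The exact paired t test gives 16.8, so 17, with power 74.8% at 15. In either case the number was set for a mean change in SUV, not for a logistic model.

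**2. Patients per candidate.** The resectable share at 6 months is not given. Section 9.1 describes patients as ineligible for resection at diagnosis while section 3.1 admits resectable disease; these passages need reconciling and do not settle the share. Assuming 20% to 50%, the smaller class has 3 to 7.5 of 15 patients (1.0 to 2.5 per candidate) or 4 to 10 of 20 (1.3 to 3.3 per candidate).

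**3. Simulation with no true association (true AUC 0.50).** Forward-backward stepwise logistic regression was run on three correlated normal predictors, under two sets of assumptions:

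- A: SUVmax-SUVpeak correlation 0.80-0.95, 0.5 with volume; 5 of 15 or 8 of 20 resectable.
- B: correlations 0.9 and 0.5; 3, 5 or 7 of 15, or 4 or 10 of 20 (4 of 20 at P<0.05 only).

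The looser entry rule is P<0.15 in A and AIC in B. AIC needs a likelihood-ratio statistic above 2, about P<0.16. Where two ranges are shown, the first is for P<0.05 and the second for the looser rule.

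| Result | A | B |
|---|---|---|
| Model kept | 11-17% / 33-40% | 12-18% / 34-39% |
| Mean apparent AUC when kept | 0.75-0.86 | 0.75-0.91 |
| 95% interval wholly above 0.5, all trials | 10-16% / 15-26% | not computed |
| 95% interval covers 0.50, when kept | not computed | 8-14% / 35-51% |
| Leave-one-out after selection, when kept | 0.64-0.73 | 0.64-0.78 |
| Leave-one-out, selection in every fold | 0.39-0.51 | 0.42-0.55 |

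All AUC and coverage figures in B are conditional on a model being kept. At P<0.05 they rest on 61 to 92 of 500 trials, so a coverage near 10% has a Monte Carlo standard error of up to about √(0.1 × 0.9/61) = 0.04.

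**4. Simulation with a real effect.** SUVpeak is shifted by 1.2 SD, so its own AUC is Φ(1.2/√2) = 0.80. The correlations are those of B, plus 0.95/0.7 and 0.7/0.4. In trials that keep a model:

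- The apparent AUC averages 0.84-0.94 against a true 0.76-0.78, with interval coverage 39-74%.
- Leave-one-out after selection gives 0.75-0.81, with coverage 75-93%.
- Leave-one-out with selection in every fold gives 0.63-0.71, which is too low, with coverage 63-87%. Under no association its coverage is 46-76%.

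**5. Which parameter is picked.** In step 4 the true predictor is left out of 27% (correlation 0.7), 36-43% (0.9) and 45% (0.95) of the models kept. The loss in accuracy is small. If SUVmax carries signal only through its correlation r with SUVpeak, its AUC is Φ(1.2r/√2): 0.79 at r = 0.95 and 0.78 at 0.90, a loss of 0.01-0.02. At r = 0.80 it is 0.75, a loss of about 0.05.

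**6. How much is sample size alone.** With one parameter fixed in advance, the mean AUC is 0.49-0.51 when the truth is 0.50 and 0.80-0.82 when it is 0.80. Interval coverage is still only 84-92%, and its DeLong interval excludes 0.5 in about 5-11% of trials with no association.

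**7. Width.** The Hanley-McNeil variance is [A(1−A) + (m−1)(U−A²) + (n−m−1)(V−A²)]/[m(n−m)], with U = A/(2−A) and V = 2A²/(1+A). At A = 0.80 with 5 of 15 resectable: [0.16 + 4(0.0267) + 9(0.0711)]/50 = 0.0181, so the half-width is 1.96 × 0.135 = 0.26.

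**The case against.** The strongest reply is that the plan already contains the safeguard. It prescribes leave-one-out expressly against over-fit, and the order of sentences in section 9.3 is not an algorithm. A reader might infer that the reported AUC is invalid outright. The documents do not support that: if selection is repeated in every fold, the upward bias goes. With a real effect, even leave-one-out after selection lands close to the truth (0.75-0.81 against 0.76-0.78). What remains is that the plan does not say which procedure applies, and that the ordinary interval under-covered in every version tested.

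Three further points stand.

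- Part of the interval error comes from sample size, not selection (step 6), so comparing the stepwise result with a nominal 2.5% or 5% overstates the effect of selection.
- The looser entry rule is an assumption. At P<0.05, stepwise keeps nothing in 83-89% of the trials with no association under assumptions A.
- A reader might infer that picking the wrong parameter does serious harm. With correlations of 0.9 or more, SUVmax and SUVpeak are close to interchangeable, so the objection is to claiming a ranking, not to using either one.

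A reader might also carry the point over to the primary analysis. Section 9.3 states no stepwise step for the Cox models, and resectability is absent from the objectives in sections 2.1 to 2.3.

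Simply listing three AUCs is not a cure either: with no association, at least one of three side-by-side intervals excluded 0.5 in 12-23% of trials.

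**Conclusion.** The point holds for the secondary resectability outcome and should be corrected. Stepwise selection at this size gives an optimistic apparent AUC: 0.75-0.86 on average under no association when a model is kept (assumptions A), and 0.84-0.94 against a true 0.76-0.78 under the assumed effect. The ordinary 95% interval then covers far less than 95%. Whether the final reported AUC is biased upward depends on a fold procedure that the plan leaves open; the interval problem does not. The data cannot reliably separate SUVmax from SUVpeak, so no parameter should be called the most correlated.

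The sizes rest on assumed correlations, outcome split, effect size and entry rule. Their direction was the same across every setting tried, and 20 patients did only somewhat better than 15.

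**What to change.** - Delete the stepwise sentence in section 9.3.
- Name one FLT parameter in advance as the lead for this outcome, and report its AUC with a confidence interval by a stated method.
- Report the other two single-parameter AUCs, with paired differences between parameters, as exploratory and adjusted for three comparisons (for example, limits at 1 − 0.05/3 = 98.3%).
- If a selected model is kept, label it exploratory. State the entry and stay rule, repeat the selection inside every leave-one-out fold or bootstrap resample, take the reported AUC and interval from that resampling, and report how often each parameter is chosen.

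The cost is SAP wording only, with no added scan, visit or data. The downside is that no single winning model is produced and the intervals will be wide: at an AUC of 0.80, about ±0.24 to 0.33 with 15 patients and ±0.20 to 0.28 with 20. Coverage will still fall somewhat short of 95%, and the report should say so.

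### Section 9.3: with about 15 evaluable patients, the maximum-likelihood logistic models for resectability have a material chance of no finite odds ratio if the FLT parameters discriminate

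*Combined protocol and SAP*

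**What the plan says.** Section 9.3 sets out the secondary outcome analysis: "the difference in SUVmax, SUVpeak and proliferative tumor volume between baseline and 2 cycles of chemotherapy will be correlated with binary tumor outcome". The outcome and method are given as "binary tumor outcome measured from MRI/CT (resectable versus non-resectable disease) at 6 month using logistic regression". The multiple model follows: "A multiple logistic regression with stepwise selection algorithm will be used to select the most correlated variable(s". No entry or exit threshold, direction of selection or test statistic is named.

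Two further outputs are promised: "Areas under the ROC curve (AUC) and corresponding 95% confidence interval will be calculated for all models", and "Leave one out cross validation will be applied to avoid over-fit". The second means that models are refitted with one patient left out each time.

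Section 9.2 gives the numbers available: "A sample size of 15 patients was calculated", with five more enrolled to cover dropout and absent baseline uptake, making 20. The only outcome rate in the plan is also there: "The expected response to therapy was assumed to be 20" per cent. It describes response to therapy. No expected share of resectable patients at 6 months is given.

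Neither section mentions separation, non-convergence, or a penalised or exact fit.

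**The concern.** Separation occurs when some combination of the predictors in a logistic model puts all resectable patients on one side and all the others on the other side. The likelihood then keeps rising as the coefficients grow, so the maximum-likelihood odds ratio is infinite and its Wald standard error and p-value mean nothing. With few patients in the smaller class and up to three predictors, this can happen by chance. It happens more often when the predictors really differ between the groups.

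The analysis is therefore most fragile in the situation the trial hopes for. Odds ratios and intervals could be unavailable. If selection used Wald tests, a perfect predictor could even be thrown out. In 478 simulated data sets in which one predictor separated the groups perfectly, its Wald p-value after 12 Newton steps had a median of 0.84 and was never below 0.05.

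**Working it through.** **1. The plan's sample size.** Inputs from Section 9.2: difference 0.124, SD 0.17, two-sided 5% level, 80% power.

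n = ((1.960 + 0.842) × 0.17 / 0.124)² = 14.75, so 15; and 15 + 5 = 20.

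This reproduces the plan's figures by the normal formula. (The noncentral t gives 17, with 74.8% power at 15; that is a separate matter.) The calculation concerns the mean change in SUV and says nothing about a logistic model.

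**2. Assumptions that the documents do not supply.**
- Normally distributed predictors, with correlation 0.9 between the SUVmax and SUVpeak changes and 0.5 of each with the volume change.
- All three parameters shifted equally between resectable and non-resectable patients, by 0, 1 or 1.5 SD. For one marker, AUC = Φ(shift/√2), which gives 0.50, 0.76 and 0.86. The three together have a joint AUC of about 0.79 and 0.89 at the two non-zero shifts.
- 3 to 7 of 15 resectable. What matters is the size of the smaller class, so 8 to 12 of 15 gives the same range.
- Forward selection with score-test entry at p<0.05, since the plan names no rule.

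**3. Test for separation.** Let sᵢ = +1 for resectable and −1 otherwise, and zᵢ = (1, predictors). A linear programme maximises Σ sᵢzᵢ′β subject to sᵢzᵢ′β ≥ 0 for every patient and bounded β. If the maximum is positive, no finite maximum-likelihood estimate exists.

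**4. Share of simulated data sets with no finite estimate, n = 15.** Each range runs over 3 to 7 resectable; where both ends are known they are shown as 3 of 15 / 7 of 15.

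| Model | No effect | AUC 0.76 | AUC 0.86 |
|---|---|---|---|
| Forward selection | 2% / 0% | 11% / 5% | 30% / 15% |
| All three parameters | 12% / 2% | 34% / 12% | 58% / 35% |
| One parameter | near 0% | 2-3% | 6-15% |

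These are approximate. Repeat runs of the three-parameter model at 3 of 15 gave 34-36% at AUC 0.76 and 56-61% at AUC 0.86.

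**5. Sensitivity.**
- All 20 evaluable, 4 to 9 resectable: forward selection reaches a separated model in about 2-6% at AUC 0.76 and 6-14% at AUC 0.86.
- Looser entry, p<0.15, n = 15: 7%, 22% and 42% with 3 resectable, and 1%, 7% and 28% with 7, at the three shifts.
- A separate simulation at other AUCs gave, for forward selection, 0-1% at 0.5, 9-21% at 0.8 and 30-39% at 0.9.
- Leave-one-out: if the three-parameter model is refitted each time, at least one fit (full data or refit) has no finite estimate in 14-64% of data sets at AUC 0.5, 60-90% at 0.8 and 94-97% at 0.9. These figures are for the forced three-parameter model, not the selected one.

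**6. Check of the remedy.** Firth-penalised fits converged to finite estimates in 1136 of 1136 separated data sets.

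**The case against.** The strongest objection is that the alarming rates belong to a model the plan may never report. Section 9.3 plans selection, and selection often stops at one variable. The 34% and 58% for the three-parameter model at 3 of 15 then overstate the risk. This stands: the forward-selection row is the one to read, with the one-parameter row for the simple models. The rate there is lower but not negligible once the parameters discriminate.

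A reader might infer several stronger things that the documents do not support.

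- **That 3 of 15 is the planned resectable share.** The 20% in Section 9.2 is a response rate. Sections 2.1 and 3.1 also admit patients resectable at presentation, while Section 9.1 describes patients who cannot be resected at diagnosis, so the share cannot be deduced. Only a range is defensible.
- **That the whole secondary analysis fails.** The outputs named for it are selected variables, AUCs with intervals and cross-validation. An AUC can be computed under separation, although the apparent value is then 1.
- **That stepwise selection must run on Wald p-values.** No criterion is named. Score, likelihood-ratio or information-criterion selection would not depend on them.
- **That the model should be cut to one pre-named parameter.** This would lower the rate, but it drops the plan's stated aim of finding which parameter is most related to the outcome. That is a change of question and a debatable trade.

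It is also fair to say that the stakes are limited. Resectability is not among the objectives or endpoints in Section 2 and appears only as a secondary outcome variable in Section 9.3.

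**Conclusion.** The point holds in a limited form. If the FLT parameters discriminate, the planned maximum-likelihood fits have a material chance of giving no finite odds ratio or Wald interval. With 15 evaluable patients the forward-selected model is affected in about 5-11% of data sets at a single-marker AUC of 0.76 and 15-30% at 0.86; with an uninformative marker, in about 0-2%. If all 20 are evaluable, the risk at the same two AUCs falls to about 2-6% and 6-14%.

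These figures rest on the assumed resectable share, correlations, equal shifts and entry rule, none of which is in the documents. The direction, more separation with better discrimination, held in every setting tried. It would be wrong to conclude that the estimates usually fail whatever the marker does, or that the Cox primary analysis is affected. That analysis was not examined here.

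**What to change.** In Section 9.3, state that the single-predictor and multiple logistic models for resectability will be fitted by Firth penalised likelihood, with profile penalised-likelihood confidence intervals. Use penalised likelihood-ratio tests for any selection step, and the same fit in each leave-one-out refit. The aim of selecting among the three parameters can stay.

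The cost is a change of wording and a different fitting routine; no patient, scan or visit is affected. The statistical price is that odds ratios are pulled toward 1 and predicted probabilities toward 0.5, by an amount not computed here. Firth makes the estimates exist. It does not cure the imprecision that comes from 3 to 7 patients in the smaller class, and the report should say so.

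### Leave-one-out AUCs for the logistic resectability models in Section 9.3, if pooled across fits as the wording naturally implies, fall well below the true value with about 15 patients

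*Combined protocol and SAP*

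**What the plan says.** Section 9.3 relates the FLT changes to a "binary tumor outcome measured from MRI/CT (resectable versus non-resectable disease) at 6 month using logistic regression". The candidates are the changes in SUVmax, SUVpeak and proliferative tumor volume, and a stepwise multiple logistic regression picks among them. The section then states "Areas under the ROC curve (AUC) and corresponding 95% confidence interval will be calculated for all models" and, directly after, "Leave one out cross validation will be applied to avoid over-fit".

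The Study Summary repeats the AUC and cross-validation sentences. There they follow the Cox models, and resectability is not mentioned.

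On numbers, Section 9.2 states "A sample size of 15 patients was calculated using a two-sided paired t test" and "Five patients were added to the sample size to compensate for dropout and no uptake on the baseline scan", which gives 20 enrolled.

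The plan does not say:
- whether the reported AUC is the cross-validated one;
- how held-out predictions are combined;
- whether stepwise selection is repeated in each fold;
- which method gives the confidence interval.

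**The concern.** An AUC compares resectable with non-resectable patients, so it needs at least one of each. A leave-one-out fold holds one patient. A leave-one-out AUC must therefore rank 15 predictions that come from 15 different fits, and those fits differ systematically. Removing a resectable patient lowers the proportion resectable in the training data, and with it that patient's own predicted risk. Removing a non-resectable patient raises it. The held-out scores are pushed against the truth even when the model has one predictor and hardly over-fits.

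At stake is the AUC and interval for whether FLT change separates resectable from non-resectable disease at 6 months. A moderately useful marker could be reported as no better than chance, in a small study whose purpose is to judge whether the marker merits further work.

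**Working it through.** **Inputs.** From Section 9.2: 15 evaluable, 20 enrolled, difference 0.124, SD 0.17, two-sided alpha 0.05, power 80%. From Section 9.3: logistic model, three FLT parameters, stepwise selection, leave-one-out, AUC. The documents give no resectable fraction. I assume 3, 5 or 7 of 15; the 3 matches the 20% response rate in Section 9.2. Normally distributed markers are also assumed, as is a correlation of 0.7 between markers where three are used.

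**1. The plan's own figure.** n = [SD × (z₀.₉₇₅ + z₀.₈₀) / δ]² = [0.17 × (1.960 + 0.842) / 0.124]² = 14.8, rounded up to 15. The stated size is reproduced by the normal formula. The exact t calculation gives power 0.748 at 15 and reaches 0.806 at 17. The plan states no figure for the AUC.

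**2. Mechanism.** Take 5 resectable of 15. Without a resectable patient the training proportion is 4/14 = 0.286. Without a non-resectable patient it is 5/14 = 0.357. A model with no predictor would then score every resectable patient below every non-resectable one, a pooled AUC of 0. A weak marker only partly offsets this shift. Leave-pair-out removes one patient of each kind, so the training proportion is 4/13 = 0.308 in every fit and the shift disappears.

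**3. Size, one marker, n = 15.** Marker separation was set to give a known true AUC. The logistic model was refitted 15 times, and the rank AUC was taken over the pooled held-out linear predictors (600 trials per cell, Monte Carlo standard error about 0.01).

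| True AUC | Mean pooled AUC, 3 / 5 / 7 resectable | Share of trials at or below 0.5 |
|---|---|---|
| 0.50 | 0.23 / 0.26 / 0.27 | 80 / 77 / 76% |
| 0.70 | 0.41 / 0.46 / 0.48 | 57 / 50 / 42% |
| 0.80 | 0.55 / 0.64 / 0.64 | 34 / 19 / 17% |
| 0.90 | 0.74 / 0.79 / 0.82 | 9 / 4 / 1% |

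Repeated runs gave 0.23-0.28, 0.4-0.5, 0.55-0.67 and 0.74-0.82 for the four rows. At a true AUC of 0.80, the lower 95% limit (Hanley-McNeil standard error, assumed) exceeded 0.5 in 17 / 28 / 34% of trials for the pooled AUC, against 47 / 62 / 64% for the marker's own rank AUC.

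**4. Is pooling the cause?** On the same data sets (5 resectable of 15, 100 trials), pooled leave-one-out averaged 0.267 and 0.631 for true 0.50 and 0.80. Leave-pair-out averaged 0.487 and 0.775. The model and data are the same, so the pooling is the cause.

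**5. Several markers, n = 15.** With three markers and no selection, the mean pooled AUC was 0.32-0.40 for useless markers and 0.56-0.67 when each had a true AUC of 0.80 (300 trials). With forward stepwise selection redone in each fold (120 trials), it was 0.05-0.08 for useless markers (median 0, the no-predictor case of step 2), 0.45-0.56 at 0.80 each, and 0.68-0.80 at 0.90 each.

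**6. All 20 evaluable.** One marker: 0.23-0.29 when useless and 0.62-0.71 at true 0.80. Full retention does not cure it.

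**7. Cox scores.** A one-covariate Cox model has no intercept to shift. With n = 15 and death before the median time as the outcome, pooled leave-one-out gave 0.45 for a useless marker, 0.77 where the marker's own AUC was 0.79, and 0.85 where it was 0.86.

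**The case against.** The best reply is that the plan never says the reported AUC comes from held-out predictions. The AUC sentence and the cross-validation sentence are separate. Leave-one-out could serve model choice or an error rate, with apparent AUCs reported. This stands as a limit on certainty: the bias follows on the natural reading, not on every reading. It does not rescue the text, because an apparent AUC after stepwise selection is not corrected for over-fit, which is the stated purpose.

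A reader might infer more than the documents support:

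- **That a good marker will look useless.** This fits a single marker with true AUC near 0.70, or about 0.80 with stepwise selection in each fold. A single marker at 0.80 to 0.90 is lowered but usually stays above 0.5.
- **That 0.25 is the general null value.** It belongs to the one-predictor logistic model; steps 5 and 7 give other values.
- **That all planned AUCs, or the primary analysis, are compromised.** Cox scores are barely affected and the Cox p-values not at all. Sections 2.1 to 2.4 name overall and progression-free survival. Resectability is a secondary outcome variable only in Section 9.3.
- **That single-parameter AUCs need no caution once cross-validation is dropped.** Choosing the best of three does bias the result: with correlation 0.7 (assumed), the best of three useless markers averages 0.58-0.60, and the best of three at true 0.70 averages 0.77-0.79.

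The alternatives are not perfect either. Leave-pair-out averaged 0.63-0.69 for a true 0.70, and percentile-bootstrap intervals at n = 15 covered a true 0.80 in only 82-90% of trials.

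**Conclusion.** The concern holds for the logistic resectability models in Section 9.3, on the natural reading that held-out predictions are pooled. At n = 15 the mean AUC of a one-marker model is lowered by roughly 0.22-0.27 when the true value is 0.50, 0.2-0.3 at 0.70, 0.13-0.25 at 0.80 and 0.08-0.16 at 0.90. For useless markers and for markers of 0.80 each, the loss is greater under stepwise selection repeated in each fold. These sizes rest on the assumed resectable count, normal markers and, for several markers, the assumed correlation. The direction follows from the arithmetic of the left-out patient.

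This is more than missing detail, because following the text as naturally read gives a misleading number. It is a should-fix: the affected analysis lies outside the stated objectives, and the survival analyses are largely spared.

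**What to change.** In Section 9.3, replace the leave-one-out sentence with wording such as:

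> Pooled leave-one-out AUCs will not be used for the logistic models. For each single FLT parameter, the rank AUC of the percentage change will be reported with a 95% confidence interval, with its direction fixed in advance (larger decrease taken to favor resectable disease). All three parameters will be reported, and the best of the three will not be presented as an unbiased estimate. For the multiple or stepwise logistic model, the AUC will be corrected by leave-pair-out cross-validation or by bootstrap optimism correction, repeating variable selection in every resample. Intervals at about 15 patients are approximate.

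The final text should name one of the two corrections and the interval method before outcomes are analyzed. In the Study Summary, refer to the Section 9.3 method and do not carry the resectability wording into the Cox models.

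Cost: SAP wording, a few lines of code and somewhat more computation (with 5 resectable of 15, leave-pair-out needs 5 × 10 = 50 fits in place of 15). No new data are needed. The small-sample intervals remain approximate under any method.
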